2.2 PHASES, PERIODS AND TIME POINTS

2.2.1 *Phases and periods*

All events and assessments will be allocated to phases and periods (see Table 1). A patient can start in 1705 in an inter-treatment period or in a cycle, depending on the patient status regarding the need for (re-)treatment upon roll-over. Each period following ITPO coincides with a cycle and includes the 4 administrations of efgartigimod and the inter-treatment period (ITP) visits. The length of the ITP is patient specific and can differ between the different periods. The number of patients may decline for each subsequent cycle.

	Statistical Analysis Plan	
ARGX-113-1705	Final Analysis	Final 1.0 of 20SEP2022

Table 1: phase/period definition

Phase	Period	Start	End
Treatment	ITP0	Earliest of (date of signing the informed consent form (ICF) and date of roll-over), with 00:00 added as time part.	First administration date/time in cycle 1 – 1 minute
	Cycle 1	First administration date/time in cycle 1	First administration date/time in next cycle – 1 minute or if last cycle: date of last contact, with 23:59 added as time part
	Cycle n	First administration date/time in cycle n	First administration date/time in next cycle – 1 minute or if last cycle: date of last contact, with 23:59 added as time part
	Cycle x	First administration date/time in cycle x	Date of last contact, with 23:59 added as time part

AEs and concomitant medications will be allocated to phases and periods as described in sections 5.1.2 and 3.5.2 respectively. All other assessments will be allocated to phases and periods based on the assessment date/time.

In case of (partially) missing date/time fields disabling allocation or date(time) equal to dosing date(time), information from visit label and protocol schedule of assessments (SoA) will be used to allocate to the correct period. If this is not possible, assessments will be allocated to the first possible cycle (not ITP0) unless the available parts of the assessments start or stop date/time provide evidence the assessments did not occur during that period.

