2.4 PRESENTATION OF RESULTS

2.4.1 Calculation of descriptive statistics and percentages

In tables by analysis visit, only analysis visits with at least 10 subjects (overall) will be shown.

For continuous variables, full descriptive statistics will only be presented if there are at least 2 non-missing observations. Alternatively, only the number of non-missing data points and mean are shown.

	
Statistical Analysis Plan
	

ARGX-113-1705
	
Final Analysis
	
Final 1.0 of 20SEP2022

Descriptive statistics will include the number of non-missing data points, the arithmetic mean, the standard deviation (SD), the median, minimum, Q1, Q3 and maximum.

Mean, median, Q1 and Q3 will be presented with one more decimal place than the individual values. SD will be presented with two more decimal places than the individual values. Minimum and maximum will be presented with the same number of decimal places as the individual values.

For event-type safety data, the number and percentage of patients with an event will be shown. The denominator will be all patients in the analysis set per treatment and cycle. All cycles will be shown, even if no events are present.

For frequency tabulations and cross-tabulations, the denominator will be all patients in the analysis set per treatment. For tables where results are shown by analysis visit, the denominator will be all patients in the analysis set per treatment and per analysis visit. Missing values will never be included in the denominator count when computing percentages. For cross-tabulations of post-baseline results versus baseline results, a ‘missing’ category will be shown for baseline results if applicable.

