5. SAFETY ANALYSES

5.1 ADVERSE EVENTS

5.1.1 *Available data*

Adverse events (AEs) are coded into system organ classes and preferred terms using the MedDRA version 24.1 (SEP2021). AEs were graded using the National Cancer Institute (NCI) Common Terminology Criteria for Adverse Events (CTCAE) version 5.0. For each AE, start and stop date/times are collected as well as severity, a seriousness flag, treatment relatedness, relatedness to procedures, action taken towards the study drug and outcome.

5.1.2 *Derivation rules*

Based on their start date/time, AEs will be allocated to the analysis period during which they started. Each AE will therefore be reported in only one period. Periods are defined in section 2.2.1. In case the AE start date/time is incomplete or missing and the AE could consequently be allocated to more than one period, AE will be allocated to the first possible cycle unless the available parts of the AE start or stop date/time provide evidence the assessments did not occur during that period.

Event rates per patient years of follow-up (PYFU) will be defined as the number of events divided by the sum of follow-up time (i.e. duration of treatment phase) of all participants per treatment expressed in years.

A death case is defined as an AE with outcome ‘fatal’.

Adverse events of special interest will be defined using MedDRA SOC ‘Infections and infestations’.

Infusion-related reactions (IRR) will be defined as all AEs with a MedDRA preferred terms that are listed in either:

- MedDRA Hypersensitivity SMQ broad selection
- MedDRA Anaphylactic reaction SMQ broad selection
- MedDRA extravasation events (injections, infusions and implants) SMQ broad selection, excluding implants

AND occurring within 48 hours of an infusion, or within 2 days in case no AE start time is available.

An AE for which the study drug was discontinued is defined as an AE with action taken ‘drug withdrawn’.

Treatment-relatedness will be dichotomised as follows in tables:

- Treatment-related: related, probably related, possibly related or missing
- Not treatment-related: not related, unlikely related, not applicable

	
Statistical Analysis Plan
	

ARGX-113-1705
	
Final Analysis
	
Final 1.0 of 20SEP2022

AE onset and duration will be calculated as follows when start and stop dates are fully known

- AE onset day (vs. first administration)

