5.1.3 Presentation of results

Adverse events occurring in ITP0 will only be listed. AEs will be tabulated by AChR-Ab status and overall and within AChR-Ab status, by cycle and overall.

An overview table will show the number and percentage of patients with at least one event, the number of events and event rates per patient years of follow-up for the following:

- TEAEs
- Serious TEAEs
- Grade ≥ 3 TEAEs
- TEAEs of special interest
- IRR events
- Fatal TEAEs
- Treatment-related TEAEs according to the Principle Investigator
- Procedures-related TEAEs according to the Principle Investigator
- Serious treatment-related TEAEs
- TEAEs for which the study drug was discontinued

Summary tables by MedDRA system organ class and preferred term will show the number and percentage of patients with at least one event. The table of TEAEs will additionally show the number of events.

	
Statistical Analysis Plan
	

ARGX-113-1705
	
Final Analysis
	
Final 1.0 of 20SEP2022

Separate tables will be prepared for the following TEAEs:

- Serious TEAEs
- Non-serious TEAEs
- Grade ≥ 3 TEAEs
- IRR events
- Treatment-related TEAEs
- Procedures-related TEAEs
- Serious treatment-related TEAEs
- Serious IRR events
- TEAEs for which the study drug was discontinued

All AEs, including pre-treatment events will be listed.

COVID related events (events with preferred term COVID-19, COVID-19 pneumonia, suspected COVID-19 and coronavirus infection) will be listed. This listing will include all collected AE information and additionally the cycle, onset since first efgartigimod dose, onset since last efgartigimod dose before AE onset, last total IgG before AE onset, the last percent change in total IgG before AE onset and the time when that reported total IgG was taken compared to AE onset.

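### Adverse event tables by system organ class and preferred term show crude percentages without person-time, and the SAP's patient-year denominator does not match the columns of the tables

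*SAP*

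**What the plan says.** SAP 5.1.3 sets the content of the SOC/PT tables: "Summary tables by MedDRA system organ class and preferred term will show the number and percentage of patients with at least one event". One table gets more: "The table of TEAEs will additionally show the number of events". All adverse event tables are split the same way: "AEs will be tabulated by AChR-Ab status and overall and within AChR-Ab status, by cycle and overall". For these percentages SAP 2.4.1 uses a head count: "The denominator will be all patients in the analysis set per treatment and cycle".

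Exposure adjustment does exist, but only in the overview table (14.3.1.1). There the SAP plans "the number of events and event rates per patient years of follow-up for the following" ten categories, among them events of special interest and infusion-related reactions (IRRs). SAP 5.1.2 gives the denominator of the rate as the "sum of follow-up time (i.e. duration of treatment phase) of all participants per treatment expressed in years".

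On observation time, SAP 2.2.1 says of the intertreatment period: "The length of the ITP is patient specific and can differ between the different periods". The same section runs a patient's last cycle to the date of last contact and places ITP0 inside the treatment phase. SAP 5.1.3 only lists ITP0 events. SAP 3.1 plans study-duration categories from under 168 days to 1081–1262 days.

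**The concern.** Under any steady hazard, the share of patients with at least one event depends on the rate multiplied by the time observed. The columns of these tables differ in time observed, and the tables do not show it. A percentage that changes from one cycle to the next may reflect a change in risk or only a change in cycle length. An overall percentage pools patients followed for months with patients followed for about three years.

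This matters because the trial has one arm and its primary question is long-term safety in AChR-Ab seropositive patients. Protocol 4.2 says that safety is to be evaluated over the whole trial and by cycle, so the by-cycle columns are meant to be read. The SOC/PT tables are where a reader looks for a particular infection or another specific event.

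The overview rates raise a second problem. Their denominator is defined once per treatment, for the whole treatment phase, and it has no stated counterpart for a cycle or an antibody subset.

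**Working it through.** The documents give no adverse event rate or percentage, so there is no figure of the plan to reproduce. The event rates below are assumptions.

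**Inputs from the documents**
- Shortest nominal Part B cycle: visit 4 at X+21 (Protocol Table 2) plus at least 4 weeks (Protocol 4.1), so 21 + 28 = 49 days.
- Part A: 365 days, used here as an example of a long cycle.
- Upper bound of the shortest follow-up category: 168 days (SAP 3.1). Maximum planned duration: 1095 days (Protocol Table 2).

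**Step 1. Same rate, different time.** For a constant rate λ per patient-year, P(at least one event in d days) = 1 − exp(−λ·d/365.25).

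| λ | 49 days | 168 days | 365 days | 1095 days |
|---|---|---|---|---|
| 0.05 | 0.7% | 2.3% | 4.9% | 13.9% |
| 0.2 | 2.6% | 8.8% | 18.1% | 45.1% |
| 1.0 | 12.6% | 36.9% | 63.2% | 95.0% |

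With no difference in risk, the percentage is 5.0 to 7.3 times higher in 365 days than in 49 days, and 2.6 to 6.1 times higher in 1095 days than in 168 days.

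**Step 2. The order can reverse.** A rate of 0.4 in a 49-day cycle shows 5.2%. Half that rate, 0.2, over 365 days shows 18.1%.

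**Step 3. Cycle number and cycle length are linked.** Reaching cycle 10 within 1095 days requires the first nine cycles to average at most 1095/9 = 121.7 days. A patient who is never retreated contributes a single cycle 1 that lasts until last contact. The early columns therefore mix long and short cycles, and the late columns hold only patients whose preceding cycles were short on average.

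**Step 4. What a rate shows instead.** Take 100 patients and λ = 0.2. Expected events are 2.7 in 13.4 patient-years (49 days), 20.0 in 99.9 (365 days) and 60.0 in 299.8 (1095 days). Each gives 20 per 100 patient-years.

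**Step 5. The SAP 5.1.2 denominator.**
- *By cycle.* Suppose the same 100 patients are followed for 365 days and one cycle lasts 49 days. The 2.7 events of that cycle over whole-phase time of 99.9 patient-years give 2.7 per 100 patient-years. Over the cycle's own 13.4 patient-years they give 20.
- *By antibody status.* Seropositive events divided by the time of all participants understate the rate by the share of time that seronegative patients contribute.
- *ITP0.* Its time is counted and its events are not. An assumed 90-day ITP0 multiplies a patient's rate by 275/365 = 0.753 when the phase lasts 365 days, and by 1005/1095 = 0.918 when it lasts 1095 days.

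**The case against.** The best defence is that the plan does what the protocol asks and somewhat more. The endpoint is incidence and severity, and Protocol 8.4.1 specifies frequency tables by cycle and overall. The percentage per cycle is a legitimate measure of risk per treatment course. A yearly rate mixes the three dosing weeks with time off drug and is easiest to read under a constant hazard. Cycle duration is tabulated by antibody status (14.1.1.5 and 14.1.1.6) and study duration separately (14.1.1.7 and 14.1.1.8). The analysis is descriptive, so no test goes wrong.

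Much of this stands. It supports keeping the percentages. For the all-TEAE table a reader could even work out rates, because event counts are planned and the cycle-duration tables give a number and a mean, whose product is person-time. No counts are planned for the serious, non-serious, grade 3 or higher, treatment-related, procedure-related, serious related and discontinuation tables, so the same calculation is impossible there.

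Four stronger readings are tempting, and the documents do not support them:
- *That the SAP ignores exposure.* It plans rates for ten categories. Events of special interest are the whole infections SOC, so that SOC already has a rate. The gap is at PT level and in the other SOCs.
- *That follow-up confounds the two 1704 treatment groups.* Both enter under the same criteria and share the same end-of-study rule. Nothing shows that their follow-up differs.
- *That late cycles will look safer.* Step 3 shows a constraint on the preceding cycles. No typical lengths are given, and a late cycle that is a patient's last runs to last contact.
- *That every SOC/PT table needs a person-time rate.* An IRR counts only within 48 hours of an infusion (or 2 days if no start time is recorded), so cycle person-time would make long cycles look safer at the same risk per infusion.

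**Conclusion.** The point holds as a weakness in interpretation of the main safety tables, and it should be corrected. The percentages in the SOC/PT tables other than the IRR tables cannot be compared across cycles, and overall they lack a time frame. The size depends on assumed constant rates and on the chosen lengths of 49 and 365 days. The ratio is about 5 to 7 throughout, but the absolute gap is 4.2 points at 0.05 per patient-year (4.9 − 0.7), 15.5 at 0.2 (18.1 − 2.6) and 50.6 at 1.0 (63.2 − 12.6). For rare preferred terms the gap in points is small. How far actual cycle lengths differ is not known from the documents.

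The mismatch in the patient-year definition needs no assumption about rates. As written, it has the wrong denominator for by-cycle columns and for the antibody subsets, and it counts ITP0 time without ITP0 events. A programmer might use matching person-time anyway, but the SAP does not say so.

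**What to change.** - Keep the percentages in all tables.
- In tables 14.3.1.2 to 14.3.1.9, add events per 100 patient-years, and add event counts where they are not already planned (14.3.1.3 to 14.3.1.9).
- Redefine patient-years of follow-up in SAP 5.1.2 so that person-time matches each column (cycle, AChR-Ab subset and treatment) and starts at the first dose in 1705, which excludes ITP0. Apply this definition in overview table 14.3.1.1 as well.
- Leave IRR tables 14.3.1.10 and 14.3.1.11 as percentages, or express them per infusion.

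The cost is extra columns. Event start dates, cycle boundaries and durations are already derived for other tables, so no new data are needed. The drawbacks are longer tables and unstable rates in late cycles with few patients, which a footnote can flag.

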5.2 CLINICAL LABORATORY EVALUATION

5.2.1 Available data

Per protocol, for part A, the following laboratory parameters are expected:

- Biochemistry: Creatinine, creatinine clearance (BSA unadjusted), blood urea nitrogen (BUN), glucose, glycosylated haemoglobin (HbA1c), alanine aminotransferase (ALT), aspartate aminotransferase (AST), total bilirubin, gamma-glutamyl transferase (GGT), C-reactive protein (CRP), alkaline phosphatase (ALP), lactate dehydrogenase (LDH), uric acid, albumin, potassium, sodium, total calcium, lipid panel (total cholesterol, high density lipoprotein (HDL), low density lipoprotein (LDL), and triglycerides), international normalized ratio (INR) and activated partial thromboplastin time (aPTT).

Note: for lipids and glucose, only fasted samples (fasting status Y) will be considered

- Haematology: Haemoglobin, platelet count, white blood cell (WBC) count with WBC differential
- Urinalysis: Colour, clarity/appearance, specific gravity, pH, protein, glucose, ketones, blood, bilirubin, urobilinogen, nitrite, leukocyte esterase, and microscopic examination including red blood cell (RBC) count, WBC, cast crystals, bacteria.

Normal ranges are available as provided by the laboratory.

For part B, laboratory samples are analysed locally. Results are not entered in the clinical database, but in case of a clinically significant abnormal result, it is reported as an adverse event.

	
Statistical Analysis Plan
	

ARGX-113-1705
	
Final Analysis
	
Final 1.0 of 20SEP2022

5.2.2 Derivation rules

The following parameters will be derived:

- Estimated glomerular filtration rate (eGFR) (Chronic Kidney Disease Epidemiology Collaboration (CKD-EPI)) (mL/min/1.73m²) = $141 * \text{minimum}(\text{creatinine } (\mu\text{mol/L}) / (88.4 * K); 1)^\alpha * \text{maximum}(\text{creatinine } (\mu\text{mol/L}) / (88.4 * K); 1) - 1.209 * 0.993^{\text{age (years)}} * [1.018 \text{ if female}] * [1.159 \text{ if race = black}]$
 where K = 0.7 if female and K = 0.9 if male;
 $\alpha = -0.329$ if female and $\alpha = -0.411$ if male
- Lipid ratios will be calculated based on fasted samples only (missing fasting status is considered as non-fasted) and rounded as detailed in section 2.3.3:
 - total cholesterol/HDL
 - LDL/HDL
 - HDL/LDL
- The following abnormality categories will be defined:
 - Low: value < lower limit of normal range
 - Normal: lower limit of normal range ≤ value ≤ upper limit of normal range
 - High: value > upper limit of normal range

Note:

- Classification will be done in standardised units, using non imputed values and limits.
- For the worst-case analysis visits, as defined in section 2.2.5, an additional category low + high is defined in case there are both low and high post-baseline values.

Toxicity grades will be computed according to the common toxicity criteria for adverse events (CTCAE) toxicity grading list. The implementation of these toxicity grades for analysis is presented in appendix 9. Only the parameters described in appendix 9 will be computed, according to the declared limits for each grade.

5.2.3 Presentation of results

The statistical analysis will present results in standardised units, except for corrected GFR, which will be reported in mL/min/1.73m².

Laboratory data will be tabulated by AChR-Ab status and overall.

Continuous laboratory parameters will be summarised by means of descriptive statistics at each analysis visit. Actual values and changes from baseline will be shown in the same table. Categorical urinalysis results will be listed only.

Laboratory abnormalities will be presented as cross-tabulations of the abnormality at each post-baseline analysis visit and at the worst-case analysis visit versus the baseline abnormality. Numbers of patients with treatment-emergent abnormalities (see Definition of terms) will also be shown. The denominator for the percentage is the total number of patients having data for the parameter per AChR-Ab status, treatment and analysis visit in the safety analysis set.

	
Statistical Analysis Plan
	

ARGX-113-1705
	
Final Analysis
	
Final 1.0 of 20SEP2022

Laboratory toxicity grades will be presented as cross-tabulations of the toxicity at each post-baseline analysis visit and at the worst-case analysis visit versus the baseline toxicity. Numbers and cumulative numbers over decreasing toxicity grading of patients with treatment-emergent toxicities will also be shown. The denominator for the percentage is the total number of patients having data for the parameter per AChR-Ab status, treatment and analysis visit in the safety analysis set. Parameters having toxicity grades defined in both directions (hypo and hyper) will be shown by direction.

All laboratory data will be listed, but only for patients with any post-baseline abnormality.

5.3 VITAL SIGNS

5.3.1 Available data

The following vital signs parameters are collected: systolic (SBP) and diastolic blood pressure (DBP) in supine position, pulse rate, body temperature and weight (only fixed on few visits, at other visits only in case of obvious weight change).

5.3.2 Derivation rules

Abnormalities are defined in below table.

	Pulse rate (bpm)	SBP (mmHg)	DBP (mmHg)	Temperature (°C)
Low	<40	<90	<45	<35.8
Normal	40-100	90-150	45-90	35.8-37.5
High	>100	>150	>90	>37.5

Note: For the worst-case analysis visits, as defined in section 2.2.5, an additional category low + high is defined in case there are both low and high post-baseline values.

5.3.3 Presentation of results

Vital signs data will be tabulated by AChR-Ab status and overall.

Vital signs parameters supine SBP, DBP and pulse rate will be summarised by means of descriptive statistics at each analysis visit. Actual values and changes from baseline will be shown in the same table.

Abnormalities will be presented as cross-tabulations of the abnormality at each post-baseline analysis visit versus the baseline abnormality and as cross-tabulations of the worst-case abnormality versus the baseline abnormality. Numbers of patients with treatment-emergent abnormalities will also be shown.

All vital signs data will be listed, but only for patients with any post-baseline abnormality.

	Statistical Analysis Plan	
ARGX-113-1705	Final Analysis	Final 1.0 of 20SEP2022

5.4 ELECTROCARDIOGRAMS

5.4.1 Available data

The following electrocardiogram (ECG) parameters will be collected: heart rate (HR), QRS interval, PR interval, QT interval, QTcF and QTcB.

5.4.2 Derivation rules

Abnormalities for HR, QRS and PR interval are defined in below table.

	HR (bpm)	PR (ms)	QRS (ms)
Low	<40	<120	-
Normal	40-100	120-220	0-120
High	>100	>220	>120

Note: For the worst-case analysis visit, as defined in section 2.2.5, an additional category low + high is defined in case there are both low and high post-baseline values.

For QTc interval (ms), the following categories are defined:

- Actual values:
 - ≤ 450 (normal)
 -]450; 480]
 -]480; 500]
 - > 500
- Changes:
 - ≤ 30 (normal)
 -]30; 60]
 - > 60

Note: The worst-case, as defined in section 2.2.5, is the highest post-baseline value and associated change.

5.4.3 Presentation of results

Uncorrected QT interval and RR will only be listed.

ECG data will be tabulated by AChR-Ab status and overall.

Continuous ECG parameters will be summarised by means of descriptive statistics at each analysis visit. Actual values and changes from baseline will be shown in the same table.

Abnormalities of the actual values will be presented as cross-tabulations of the abnormality at each post-baseline analysis visit, and at the worst-case analysis visit versus the baseline abnormality. Numbers and cumulative numbers over decreasing abnormalities (QTc only) of patients with treatment-emergent abnormalities will also be shown. The denominator for the percentage is the total number of patients having data for the parameter per AChR-Ab status, treatment and analysis visit in the safety analysis set.

	
Statistical Analysis Plan
	

ARGX-113-1705
	
Final Analysis
	
Final 1.0 of 20SEP2022

Abnormalities of the QTc changes will be presented as tabulations of the change abnormality at each post-baseline analysis visit and at the worst-case analysis visit. Cumulative numbers over decreasing change abnormalities of patients will also be shown. The denominator for the percentage is the total number of patients having data for the parameter per AChR-Ab status, treatment and analysis visit in the safety analysis set.

All ECG data will be listed, but only for patients with any post-baseline abnormality.

